## **5.2.4 Permanent Discontinuation of Ipilimumab**

### **5.2.4.a Permanent Discontinuation for Related Adverse Events**

Refer to Appendix B for algorithms recommended for utilization in CA184-187.  
Permanently discontinue treatment for any of the following:

- Persistent moderate adverse reactions or inability to reduce corticosteroid dose to 7.5 mg prednisone or equivalent per day.
- Severe or life-threatening adverse reactions, including any of the following:
  - Radiographic or histologic diagnosis of colitis with abdominal pain, fever, ileus, or peritoneal signs; increase in stool frequency (7 or more over baseline) or incontinence unable to be mitigated with corticosteroids, gastrointestinal hemorrhage, or gastrointestinal perforation
  - Aspartate aminotransferase (AST) or alanine aminotransferase (ALT) >5 times the upper limit of normal or total bilirubin >3 times the upper limit of normal
  - Stevens-Johnson syndrome, toxic epidermal necrolysis, or rash complicated by full thickness dermal ulceration, or necrotic, bullous, or hemorrhagic manifestations
  - Severe motor or sensory neuropathy, Guillain-Barré syndrome, or myasthenia gravis
  - Severe immune-mediated reactions involving any organ system (eg, nephritis, pneumonitis, pancreatitis, non-infectious myocarditis)
  - Immune-mediated ocular disease that is unresponsive to topical immunosuppressive therapy (eg, ocular steroids)
  - Any adverse event, laboratory abnormality or intercurrent illness which, in the judgment of the investigator, presents a substantial clinical risk to the patient with continued dosing.
  - The development of progression (irPD) in the global tumor burden confirmed by serial imaging 4-6 weeks later and/or clinical deterioration of subject's condition such that further benefit from ipilimumab dosing is unlikely or requires a change of therapy.

Please refer to section 5.1.7 and the IB for specific AE management algorithms.

**The following neurological adverse event requires permanent discontinuation of ipilimumab and defines unacceptable neurotoxicity:**

- Any motor neurologic toxicity  $\geq$  Grade 3 regardless of causality
- Any  $\geq$  Grade 3 treatment related sensory neurologic toxicity

Please refer to section 5.1.7 and the IB for specific AE management algorithms.

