## **Nivolumab Combined with Ipilimumab**

In the Phase 1 study CA209004, ascending doses of nivolumab have been studied concomitantly with ascending doses of ipilimumab in subjects with unresectable or metastatic melanoma. In each arm in this multi-arm study, ipilimumab was administered once every 3 weeks for 4 doses with nivolumab administered once every 3 weeks for 8 doses. Starting at week 24, ipilimumab and nivolumab were administered once every 12 weeks for 8 doses. The three initial dose-escalation cohorts consisted of Cohort 1 (nivolumab 0.3 mg/kg plus ipilimumab 3 mg/kg; n=14), Cohort 2 (nivolumab 1.0 mg/kg plus ipilimumab 3 mg/kg; n=17) and Cohort 3 (nivolumab 3.0 mg/kg plus ipilimumab 3 mg/kg; n=6). Later, the study was amended to include Cohort 2a which evaluated nivolumab 3 mg/kg plus ipilimumab 1 mg/kg (n=16). The following DLTs were observed in Cohort 1 - Grade 3 elevated AST/ALT (1 subject); in Cohort 2 - Grade 3 uveitis (1 subject) and Grade 3 elevated AST/ALT (1 subject) and in Cohort 3 - Grade 4 elevated lipase (2 subjects) and Grade 3 elevated lipase (1 subject). Based on these data, Cohort 2 was identified as the maximum tolerated dose (MTD) and Cohort 3 exceeded the MTD.

As of 15-Feb-2013, a total of 53 melanoma subjects were treated with nivolumab combined with ipilimumab in CA209004 across cohorts 1, 2, 2a, and 3. At least one AE regardless of causality has been reported in 98% of subjects treated. The most common (reported at > 10% incidence) treatment related AEs (any Grade %; Grade 3-4 %: 93; 53) are rash (55; 4), pruritus (47; 0), vitiligo (11; 0), fatigue (38; 0), pyrexia (21, 0), diarrhea (34; 6), nausea (21, 0), vomiting (11, 2), ALT increased (21; 11), AST increased (21; 13), lipase increased (19; 13), amylase increased (15, 6), headache (11, 0), and cough (13, 0).

The majority of AEs leading to discontinuation (regardless of causality) were Grade 3 or 4 (reported in 11 of 53 subjects, 21%). Grade 3 events included lipase increased, ALT increased, AST increased, troponin I increased, colitis, diverticular perforation, pancreatitis, tachycardia, renal failure acute, choroiditis, autoimmune disorder, and pneumonitis. One subject each discontinued due to Grade 4 events of blood creatinine increased and AST increased. No drug-related deaths were reported.

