### **Criteria to Resume Treatment**

Subjects may resume treatment with study drug when the drug-related AE(s) resolve to Grade  $\leq$  1 or baseline value, with the following exceptions:

- Subjects may resume treatment in the presence of Grade 2 fatigue
- Subjects who have not experienced a Grade 3 drug-related skin AE may resume treatment in the presence of Grade 2 skin toxicity
- Subjects with baseline Grade 1 AST/ALT or total bilirubin who require dose delays for reasons other than a 2-grade shift in AST/ALT or total bilirubin may resume treatment in the presence of Grade 2 AST/ALT OR total bilirubin
- Subjects with combined Grade 2 AST/ALT AND total bilirubin values meeting discontinuation parameters (Section 4.3.5) should have treatment permanently discontinued
- Drug-related pulmonary toxicity, diarrhea, or colitis, must have resolved to baseline before treatment is resumed
- Drug-related endocrinopathies adequately controlled with only physiologic hormone replacement may resume treatment

If the criteria to resume treatment are met, the subject should restart treatment at the next scheduled timepoint per protocol. However, if the treatment is delayed past the next scheduled timepoint per protocol, the next scheduled timepoint will be delayed until dosing resumes. If treatment is delayed > 6 weeks, the subject must be permanently discontinued from study therapy, except as specified in Section 5.2.3.

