### **5.2.3 Discontinuation of Study Therapy**

Subjects **MUST** be discontinued from study therapy **AND** withdrawn from the study for the following reasons:

- Any Grade 2 drug-related uveitis or eye pain or blurred vision that does not respond to topical therapy and does not improve to Grade 1 severity within the re-treatment period **OR** requires systemic treatment
- Any Grade 3 non-skin, drug-related adverse event lasting > 7 days, with the following exceptions for drug-related laboratory abnormalities, uveitis, pneumonitis, bronchospasm, diarrhea, colitis, neurologic toxicity, hypersensitivity reactions, and infusion reactions:
  - Grade 3 drug-related uveitis, pneumonitis, bronchospasm, diarrhea, colitis, neurologic toxicity, hypersensitivity reaction, or infusion reaction of any duration requires discontinuation
  - Grade 3 drug-related laboratory abnormalities do not require treatment discontinuation except:
    - Grade 3 drug-related thrombocytopenia > 7 days or associated with bleeding requires discontinuation
    - Any drug-related liver function test (LFT) abnormality that meets the following criteria require discontinuation:
      - AST or ALT > 8 x ULN
      - Total bilirubin > 5 x ULN
      - Concurrent AST or ALT > 3 x ULN and total bilirubin > 2 x ULN
- Any Grade 4 drug-related adverse event or laboratory abnormality, except for the following events which do not require discontinuation:
  - Grade 4 amylase or lipase abnormalities that are not associated with symptoms or clinical manifestations of pancreatitis. It is recommended to consult with the BMS Medical Monitor for Grade 4 amylase or lipase abnormalities.

□ Isolated Grade 4 electrolyte imbalances/abnormalities that are not associated with clinical sequelae and are corrected with supplementation/appropriate management within 72 hours of their onset

□ Any dosing interruption lasting > 6 weeks with the following exceptions:

□ Dosing interruptions to allow for prolonged steroid tapers to manage drug-related adverse events are allowed. Prior to re-initiating treatment in a subject with a dosing interruption lasting > 6 weeks, the PI will discuss feasibility with the sponsor.. Tumor assessments should continue as per protocol even if dosing is interrupted.

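### In induction, 5.2.4.a permanently stops treatment for persistent moderate and for severe reactions, while 5.2.2 and 5.2.3 allow some of the same patients to continue, and nothing says which section governs

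*Combined protocol and SAP*

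**What the plan says.** Three places in section 5.2 decide whether a patient with a drug-related event goes on.

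- **5.2.4.a** is an instruction: "Permanently discontinue treatment for any of the following". The first trigger is "Persistent moderate adverse reactions or inability to reduce corticosteroid dose to 7.5 mg prednisone or equivalent per day". The second is "Severe or life-threatening adverse reactions, including any of the following", followed by a list that this wording leaves open. No trigger is written as a toxicity grade, *persistent* is not defined, and severe reactions carry no minimum duration. The heading of 5.2.4 names ipilimumab only, but the operative line speaks of treatment.
- **5.2.2**, under the criteria to resume, is a permission: "Subjects may resume treatment in the presence of Grade 2 fatigue". Patients with no earlier Grade 3 drug-related skin event also "may resume treatment in the presence of Grade 2 skin toxicity".
- **5.2.3** requires discontinuation for Grade 3 drug-related events only when they are non-skin and last more than 7 days, or belong to a named type (such as colitis or pneumonitis) that stops treatment at any duration. Grade 3 laboratory abnormalities do not require it, apart from stated platelet and liver limits. Grade 4 events do require it, with exceptions that include "Grade 4 amylase or lipase abnormalities that are not associated with symptoms or clinical manifestations of pancreatitis".

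Section 5.2.4.b lists exceptions to permanent discontinuation: local anti-tumor inflammation, hospitalization for work-up, ocular toxicity that responded to topical therapy, and endocrinopathy controlled by replacement. No section states an order of precedence.

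**The concern.** A patient in induction with fatigue or rash that settles at Grade 2 and stays there may resume under 5.2.2, and may have to stop for good under 5.2.4.a. A patient with a Grade 3 rash, or a short Grade 3 clinical event outside the named types, need not stop under 5.2.3 but may have to under 5.2.4.a. The outcome then depends on which section the treating physician follows.

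At stake are exposure to the combination, patient safety, and the discontinuation rate. Safety and tolerability is a secondary objective in 2.2. A discontinuation rate that mixes two stopping rules describes the regimen poorly and cannot be reproduced elsewhere.

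**Working it through.** The plan gives no figure on this point, so there is none to reproduce. The check sets the rules side by side, then asks what the protocol's own frequencies can and cannot say.

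**Step 1. Severity words and grades.** Section 5.2.4.a uses *moderate* and *severe*; 5.2.2 and 5.2.3 use grades. The one place that links them is the infusion-reaction text in 5.2.6, which pairs moderate with Grade 2 and severe with Grade 3 or 4. Section 8.2 mentions intensity in its heading but defines only causal relationship. I use the 5.2.6 pairing as an assumption.

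**Step 2. Rules compared, induction.**

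| Patient | 5.2.2 / 5.2.3 | 5.2.4.a | Result |
|---|---|---|---|
| Grade 2 fatigue that does not settle | may resume | stop, if persistent | conflict |
| Grade 2 skin toxicity that does not settle, no earlier Grade 3 drug-related skin event | may resume | stop, if persistent | conflict |
| Grade 3 skin event | stop not required | stop, if severe | conflict |
| Grade 3 non-skin clinical event, 7 days or less, not a named type | stop not required | stop, if severe | conflict |
| Grade 3 laboratory abnormality outside the platelet and liver limits | stop not required | stop only if a laboratory value alone is a severe reaction | ambiguous |
| Symptom-free Grade 4 amylase or lipase | exempt | as in the row above | ambiguous |

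The exceptions in 5.2.4.b name none of these groups. The third row has further support: the condition about an earlier Grade 3 skin event in 5.2.2 makes sense only if such patients can come back to treatment, under the general requirement of Grade 1 or baseline.

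**Step 3. Scope.** If 5.2.4 stopped ipilimumab alone, nivolumab might continue. But 5.2.2 requires that in induction both drugs are delayed together and resumed on the same day, so that reading does not remove the conflict there. In maintenance only nivolumab is given, and whether 5.2.4.a applies is unclear.

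**Step 4. Frequency.** Section 1.3.6 reports 53 patients pooled over four dose cohorts (14 + 17 + 6 + 16), as percentages for any grade and for Grade 3-4. Expected count = rate × n, for 27 evaluable patients and for the accrual ceiling of 39, which includes screen failures.

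| Event | Rate | n = 27 | n = 39 |
|---|---|---|---|
| Fatigue, all Grade 1-2 (Grade 3-4 is 0%) | 38% | 10.3 | 14.8 |
| Rash, Grade 1-2 (55 − 4) | 51% | 13.8 | 19.9 |
| Rash, Grade 3-4 | 4% | 1.1 | 1.6 |
| Lipase, Grade 3-4 | 13% | 3.5 | 5.1 |

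At those rates these are ceilings, not estimates of the patients in conflict. The source does not split Grade 1 from Grade 2, persistent from transient, or symptomatic from symptom-free lipase. The pooled lipase figure, "lipase increased (19; 13" in percent, also includes the 6 patients of the cohort that exceeded the maximum tolerated dose, where three lipase events were dose-limiting. Taking 13% as 7 of 53 (0.13 × 53 = 6.9) and assuming that it contains those three, 4 of 47 remain, or 8.5%: 2.3 of 27 or 3.3 of 39, before removing symptomatic cases.

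**The case against.** **The other sections only permit; the stricter rule simply applies.** It is true that neither 5.2.2 nor 5.2.3 orders anyone to be kept on drug, so this is not a clash of two commands. But no precedence is stated, and the stricter reading would empty the Grade 2 permission for any event that persists. Section 1.3.6 does prefer the nivolumab algorithms to those in the ipilimumab brochure, but that concerns management of events, and 5.2.4.a sends the reader back to the brochure.

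**Section 5.2.4 is about ipilimumab.** This may hold for maintenance. It does not resolve induction.

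**Severe skin events in 5.2.4.a are the complicated ones on its list.** The list does name specific grave skin conditions. It is nevertheless open, and also takes in severe immune-mediated reactions of any organ.

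**Symptom-free lipase is not a severe reaction.** This largely stands. A reader might infer a direct contradiction affecting 3.5 of 27 patients. The documents do not support that: 5.2.4.a names pancreatitis and no pancreatic enzyme value, so the sections can be read together. What keeps it ambiguous is that the same list treats "Aspartate aminotransferase (AST) or alanine aminotransferase (ALT) >5 times the upper limit of normal or total bilirubin >3 times the upper limit of normal" as sufficient, and 8.1 counts abnormal laboratory findings as adverse events.

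**The response count.** A reader might also infer that stopped patients are withdrawn and their responses lost, which could matter against a threshold of 4 responders in 27. The text does not show this. Section 5.2.3 withdraws patients for its own listed reasons, and 5.2.4.a contains no withdrawal instruction. The general treatment instructions (3.2.1.c) still ask for the 12-week tumor assessment after a stop for drug-related events, 3.4 provides for later efficacy assessment by standard of care, and 6.4.3.e uses all available assessments up to subsequent therapy.

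**Conclusion.** The concern holds for induction. For persistent Grade 2 fatigue, persistent Grade 2 skin toxicity without an earlier Grade 3 drug-related skin event, Grade 3 skin events, and short Grade 3 clinical events outside the named types, the plan gives differing answers and no way to choose between them. For symptom-free enzyme rises and most other Grade 3 laboratory abnormalities the position is ambiguous, not contradictory.

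The size cannot be computed from the documents. Fatigue and rash were common in the earlier combination study, so some patients are likely to be touched, but the share is unknown. The consequence lies in exposure, safety and the discontinuation rate; no sample-size, error-rate or power figure changes, and an effect on the response count is not established. The conclusion rests on reading moderate as Grade 2 and severe as Grade 3 or 4, which the plan says only for infusion reactions; that 5.2.4.a leaves its own terms ungraded is part of the defect.

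**What to change.** Reconcile 5.2.2, 5.2.3, 5.2.4.a and 5.2.4.b:

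- Name one section that governs permanent discontinuation.
- State whether 5.2.4 applies to ipilimumab only or to all study treatment, and in which phase.
- State whether a stop under 5.2.4.a also means withdrawal from the study.
- Express the 5.2.4.a triggers as CTCAE grades with a duration, and define *persistent*.
- Say explicitly how Grade 2 fatigue and skin toxicity, Grade 3 skin and short Grade 3 clinical events, and symptom-free Grade 3-4 amylase or lipase are handled.
- Delete the conflicting lines or cross-refer them.

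The cost is an amendment to wording and a note to site staff. It can be done together with any reconciliation of the liver limits in the same sections. Which rule should stand is for the sponsor and investigators; no view is given here.

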# Hepatic Adverse Event Management Algorithm

Rule out non-inflammatory causes. If non-inflammatory cause, treat accordingly and continue I-O therapy. Consider imaging for obstruction.

[figure not shown]
Patients on IV steroids may be switched to an equivalent dose of oral corticosteroids (e.g. prednisone) at start of tapering or earlier, once sustained clinical improvement is observed. Lower bioavailability of oral corticosteroids should be taken into account when switching to the equivalent dose of oral corticosteroids.

\*I-O therapy may be delayed rather than discontinued if AST/ALT ≤ 8 x ULN and T.bili ≤ 5 x ULN.

\*\*The recommended starting dose for grade 4 hepatitis is 2 mg/kg/day methylprednisolone IV.

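### For two ranges of drug-related liver results, 5.2.4.a orders a permanent stop, 5.2.3 lists no liver criterion that requires one, and the visible Appendix A footnote allows delay; precedence and drug scope are incompletely stated

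*Combined protocol and SAP*

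**What the plan says.** **Section 5.2.4.a.** The parent section, 5.2.4, is headed for ipilimumab. The operative sentence reads "Permanently discontinue treatment for any of the following", and its list of severe or life-threatening reactions includes "Aspartate aminotransferase (AST) or alanine aminotransferase (ALT) >5 times the upper limit of normal or total bilirubin >3 times the upper limit of normal". For management it points to two places: "Refer to Appendix B for algorithms recommended for utilization in CA184-187" and "Please refer to section 5.1.7 and the IB for specific AE management algorithms".

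**Section 5.2.3.** This section governs stopping study therapy together with withdrawal from the study. On laboratory values it says "Grade 3 drug-related laboratory abnormalities do not require treatment discontinuation except". The liver exceptions that follow are "AST or ALT > 8 x ULN", total bilirubin above 5 x ULN, and "Concurrent AST or ALT > 3 x ULN and total bilirubin > 2 x ULN".

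**Appendix A, hepatic algorithm.** The flow chart is not reproduced in the text available, but its footnote is: "I-O therapy may be delayed rather than discontinued if AST/ALT ≤ 8 x ULN and T.bili ≤ 5 x ULN". The opening of Appendix A describes the algorithms as guidance to the investigator.

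**Section 5.2.6.c.** Dosing requires AST/ALT at or below 2.5 x ULN and bilirubin at or below 2 x ULN. With liver metastases the limits are 5 x and 3 x ULN. Abnormal values during treatment must be handled by the hepatotoxicity algorithm, which this section places in Appendix B.

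**Section 5.2.2.** Delay applies to every drug-related adverse event and covers all study drugs. Treatment may generally resume once the event has settled to Grade 1 or lower, or to baseline, with listed exceptions.

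**The concern.** A reader applying these sections to one laboratory report can reach opposite instructions: end treatment for good, or hold it and resume on recovery. The protocol also leaves unclear whether a stop under 5.2.4.a ends ipilimumab alone or both drugs. That matters because maintenance (numbered 3.2.1.b in the text) is nivolumab alone: one reading ends it and the other leaves it untouched.

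The situation is foreseeable. Section 1.3.6 reports Grade 3-4 rises of AST in 13% and of ALT in 11% of 53 melanoma subjects given the combination. Section 1.5 puts liver involvement at up to 95% of metastatic cases. Section 4.1 admits patients with liver metastases at AST/ALT up to 5 x ULN, which is the point above which 5.2.4.a applies. Two patients with the same drug-related result could therefore be managed differently, with consequences for exposure and for the safety description.

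**Working it through.** The documents give no figure to reproduce for this point; the check compares thresholds. Let A be the higher of AST and ALT, and B total bilirubin, both in multiples of ULN and judged drug-related.

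- 5.2.4.a: permanent stop if A > 5 or B > 3.
- 5.2.3: stop if A > 8, or B > 5, or (A > 3 and B > 2).
- Appendix A footnote: delay may replace discontinuation if A ≤ 8 and B ≤ 5.

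**Where 5.2.4.a says stop and no liver criterion in 5.2.3 is met.** This needs (A > 5 or B > 3), with A ≤ 8, B ≤ 5 and not (A > 3 and B > 2).

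- If A > 5, then A > 3, so B must be ≤ 2. Range 1: 5 < A ≤ 8 with B ≤ 2.
- If B > 3, then B > 2, so A must be ≤ 3. Range 2: 3 < B ≤ 5 with A ≤ 3.

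The ranges do not overlap, and the footnote's numeric condition holds throughout both. A grid from 0 to 12 x ULN in steps of 0.25 confirms this. Range 1 has 12 values of A times 9 of B = 108 cells, and Range 2 has 8 values of B times 13 of A = 104 cells. The total is 212, with no conflict cell elsewhere. The counts only locate the ranges; they are not patient frequencies.

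| A | B | 5.2.4.a | 5.2.3 liver criteria | Footnote condition for delay |
|---|---|---|---|---|
| 6 | 1 | stop | none met | met |
| 2 | 4 | stop | none met | met |
| 6 | 2.5 | stop | stop (combined criterion) | met |
| 9 | 1 | stop | stop | not met |

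Wherever else 5.2.4.a is triggered, 5.2.3 also requires a stop.

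**Pre-dose criteria (5.2.6.c).** With liver metastases dosing needs A ≤ 5 and B ≤ 3; without them it needs A ≤ 2.5 and B ≤ 2. Range 1 fails on A and Range 2 fails on B in either case. No dose is due at these values. The criteria do not say whether treatment has ended or may resume under 5.2.2.

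**Precedence.** Section 1.3.6 prefers the nivolumab algorithms to those in the ipilimumab IB, and 5.2.6.c makes the hepatotoxicity algorithm mandatory for abnormal values. Both lean toward the algorithm. Against that, 5.2.6.c cites Appendix B while the hepatic algorithm stands in Appendix A, Appendix A calls itself guidance, and 5.2.4.a sends the reader to the IB without saying which. No sentence ranks 5.2.3 against 5.2.4.a.

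**Frequency context.** 7/53 = 13.2% and 6/53 = 11.3% match the quoted 13% and 11%. These are Grade 3-4 rises across all dose cohorts of the earlier combination study, not counts within the two ranges.

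**The case against.** The strongest reply is that the two sections nest. Section 5.2.4 is headed for ipilimumab, and several of its sentences name that drug: the progression item and the neurological rule in 5.2.4.a, and the restart note in 5.2.4.b. Section 5.2.3 concerns leaving study therapy and the study altogether, and its sentence on laboratory values is a carve-out from the rule on Grade 3 events lasting more than 7 days, not a general permission to continue. A lower limit for ipilimumab beneath a higher limit for leaving the study is coherent. This reading is available, and if intended it removes the conflict between 5.2.3 and 5.2.4.a. The conflict with the footnote remains, because the footnote speaks of I-O therapy and Appendix A says it covers all immuno-oncology agents and regimens. The reach would then be induction only (weeks 1, 4, 7 and 10). Section 9 records 23 evaluable patients enrolled at the 2017 redesign against a target of 27, so 27 - 23 = 4 evaluable patients remained to be accrued then.

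Second, the first bullet of 5.2.4.b exempts some reversible inflammation below Grade 4 when it is attributed to a local anti-tumor reaction. With liver disease this common, an investigator might invoke it for some enzyme rises. It names no liver range and does not settle the matter in general.

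Third, the flow chart is missing from the text, so the branch to which the footnote belongs cannot be checked. That limits confidence in the footnote comparison, but not in the comparison of 5.2.3 with 5.2.4.a.

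Fourth, the pre-dose check, the hold-and-notify order set in 6.2.1 and the investigator's discretion to stop all reduce the practical risk. They do not decide between a permanent stop and resumption.

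A reader might infer more than this supports. The protocol is not silent on precedence: 1.3.6 and 5.2.6.c point one way, though incompletely. No rule here permits dosing at these values. Nor is every AST/ALT between 5 and 8 x ULN in dispute: once bilirubin exceeds 2 x ULN, both sections require a stop.

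**Conclusion.** The inconsistency is real and narrow. In the two ranges, 5.2.4.a ends treatment permanently, 5.2.3 lists no liver criterion requiring that, and the visible footnote allows delay. If 5.2.4.a covers ipilimumab only, what remains is a conflict with the footnote during induction. If it covers both drugs, it also conflicts with 5.2.3 and bears on nivolumab maintenance. Section 5.2.2 ties the drugs together for delay and resumption but does not say what happens to nivolumab after a permanent ipilimumab stop.

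The conclusion assumes that the result is drug-related, that it is not Grade 4, and that no other reason to stop applies, such as investigator judgment or an interruption beyond 6 weeks. The documents do not give the grade cut-offs, but 5.2.3 places its 8 x and 5 x limits under Grade 3, which is consistent with the second assumption.

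The number of patients affected cannot be derived from the documents. A reader might also infer a distortion of the response rate; nothing in the documents supports one, and none is claimed. This should be fixed, but it does not put the design in question.

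**What to change.** The sponsor and medical monitor should reconcile 5.2.2 (criteria to resume), 5.2.3, 5.2.4.a, 5.2.6.c and the Appendix A hepatic algorithm into one consistent set of hepatic stopping, delay and resumption rules. The text should state:

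- which section prevails where they differ;
- whether a stop under 5.2.4.a applies to ipilimumab or to both drugs, and what then happens to nivolumab;
- how the pre-dose criteria in 5.2.6.c relate to the stopping rules.

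The pointer to the hepatic algorithm (Appendix B against Appendix A) should be corrected in the same amendment. No threshold or order of precedence is proposed here; those are clinical decisions for the sponsor and medical monitor. The cost is amendment wording and notification of the study team at the single site. The sample size and the decision rule do not change.
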